7.3.2 Secondary endpoint analyses

The key secondary endpoints occurrence of adjudicated HHF (first and recurrent) will be modelled using a joint frailty model together with adjudicated CV death in order to take into account the dependence between the endpoints. The joint frailty model will be adjusted for the same covariates as the primary analysis.

The joint frailty model therefore models the hazards in the following way:

$$r_i(t | \omega_i, Z_i) = \omega_i \exp \{ \beta'_1 Z_i \} r_0(t)$$

$$\lambda_i(t | \omega_i, Z_i) = \omega_i^\alpha \exp \{ \beta'_2 Z_i \} \lambda_0(t)$$

where $r_i(t)$ is the hazard of the recurrent HHF for the i th patient, proportional to the baseline intensity function r_0 . The hazard function of CV death for the i th patient is λ_i proportional to the baseline hazard λ_0 . β_1 and β_2 are vectors of the regression coefficients of the covariate vectors Z_i including treatment, age (continuous), gender, history of DM, geographical region, LVEF (continuous) and eGFR (CKD-EPI)_{cr} at baseline (continuous). Patient specific independent random effects are denoted by ω_i , with α giving the relation between HHF and CV death.

Patient specific independent random effects denoted by ω_i and are assumed to follow a gamma distribution with mean 1.

The resulting likelihood function can be solved assuming piecewise constant hazards.

Slope in change from baseline of eGFR (CKD-EPI)_{cr} will be analysed by a random coefficient model allowing for random intercept and random slope per patient. The model will include the factors treatment, gender, geographical region, and status of DM as fixed effects and eGFR (CKD-EPI)_{cr} at baseline (continuous), LVEF (continuous), age (continuous), time, interaction of treatment by time and interaction of eGFR (CKD-EPI)_{cr} at baseline (continuous) by time as linear covariates and allow for randomly varying slope and intercept between patients. The model will include all on-treatment change from baseline data.

Since the slope is run on the change from baseline data, the intercept will model the acute drop, whereas the long-term effect is modelled by the slope.

Proprietary confidential information © 2019 Boehringer Ingelheim International GmbH or one or more of its affiliated companies

Change from baseline in clinical summary score for HF symptoms and physical limitations domains of the KCCQ at week 52 will be evaluated by a mixed model repeated measures (MMRM) model including LVEF (continuous), age (continuous) and eGFR (CKD-EPI)_{cr} at baseline (continuous) as linear covariates and baseline score by visit, visit by treatment, gender, geographical region and status of DM and as fixed effects. All on-treatment data up to week 52 will be included.

Occurrence of all-cause hospitalisation (first and recurrent) will be evaluated by a similar joint frailty as adjudicated HHF and will be evaluated with a joint model together with all-cause mortality.

The other time-to-event type of secondary endpoints will be analysed using the same Cox proportional hazards model as the primary analysis.

This also applies for time to adjudicated CV death and all-cause mortality, rather than using the joint frailty model described above.

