4. Visit dates are determined per the date of randomisation. If a visit is missed, the patient should be returned to the original visit schedule at the next visit.
5. NF = non fasting, F=fasting. Fasting means no food or liquid intake except for water the last 10-16 hours
6. All visit 1 procedures should be performed within 28 days of signing the informed consent form (ICF).
7. If accepted by local authorities or ethic committees, demographics to be collected in this trial are gender, year of birth, ethnicity and race.
8. The Investigator will be asked to record results from clinical routine examinations like ECG, echocardiography or similar procedures (MRI, CT-scan, etc.), and if applicable information gathered from interrogations of the ICD in the eCRF.
9. Vital signs measurements in this trial are blood pressure and pulse rate.
10. Protocol specified outcome events should be collected on the appropriate eCRF page. Exemptions from reporting on the SAE form are specified in [Section 5.3.7](#).
11. For patients with non-fatal stroke the Modified Rankin Scale (MRS) should be scored by the investigator based on an interview at the next regular on-site visit after the onset of the stroke. In those cases where MRS assessment occurred within 90 days after the stroke, a repeat MRS-assessment should be performed at the next on-site visit. For patients who experience a non-fatal stroke less than 90 days prior to the study closure date, the final MRS assessment will occur at the final study visit for that patient.
12. For the 12-lead ECG done at screening and EOT visit, the interpretation of the tracing must be made locally by a qualified physician or appropriately qualified designee and documented on the ECG section of the eCRF. In case of any cardiac symptoms (indicating rhythm disorders or cardiac ischaemia), additional 12-lead ECG(s) should be done to document a potential outcome event.
13. For female patients of child-bearing potential, local urine pregnancy test should be performed according to the [Flow Chart](#). More frequent testing should be performed if required by local regulations/authorities.
14. For the screening Visit 1, the safety laboratory is limited to liver transaminases, alkaline phosphatase, serum creatinine and haematology panel. Patients do not have to be fasting.
15. HbA1c to be analysed in all patients, e.g. diabetics and non-diabetics.

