5.1.2 Secondary endpoint(s)

The key secondary endpoints which are part of the testing strategy, are the following:

1. Occurrence of adjudicated HHF (first and recurrent),
2. eGFR (CKD-EPI)_{cr} slope of change from baseline

Other secondary endpoints (not part of confirmatory testing hierarchy on trial level) are the following:

- Time to first occurrence of chronic dialysis or renal transplant or sustained* reduction of $\geq 40\%$ eGFR (CKD-EPI)_{cr} or
 - sustained eGFR (CKD-EPI)_{cr} < 15 mL/min/1.73 m² for patients with baseline eGFR ≥ 30 mL/min/1.73 m²
 - sustained eGFR (CKD-EPI)_{cr} < 10 mL/min/1.73 m² for patients with baseline eGFR < 30 mL/min/1.73 m²

*An eGFR (CDK-EPI)_{cr} reduction is considered sustained, if it is determined by two or more consecutive post-baseline central laboratory measurements separated by at least 30 days (first to last of the consecutive eGFR values).

Chronic dialysis is defined as dialysis with a frequency of twice per week or more often for at least 90 days.

- Time to first adjudicated HHF
- Time to adjudicated CV death
- Time to all-cause mortality
- Time to onset of DM (defined as HbA1c $\geq 6.5\%$ or as diagnosed by the Investigator) in patients with pre-DM defined as no history of DM and no HbA1c ≥ 6.5 before treatment, and a pre-treatment HbA1c value of ≥ 5.7 and < 6.5
- Change from baseline in clinical summary score (HF symptoms and physical limitations domains) of the Kansas City Cardiomyopathy Questionnaire (KCCQ) at week 52
- Occurrence of all-cause hospitalisation (first and recurrent)

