7.3 PLANNED ANALYSES

The primary efficacy analysis will be based on the randomised set (RS), including all randomised patients.

The safety analysis will be based on the treated set (TS), which consists of all patients treated with at least one dose of the trial medication.

For both efficacy and safety analyses, treatment will be evaluated as randomised.

For serum creatinine and values based on upon this measurement such as eGFR, baseline will be defined as the mean of all available measurements from the screening visit until start of randomised trial medication.

Baseline status of DM is defined as:

- DM: any pre-treatment HbA1c above 6.5 or history of DM as entered in the eCRF on the medical history page
- Pre-DM: no history of DM and no HbA1c ≥ 6.5 before treatment and a pre-treatment HbA1c value of ≥ 5.7 and < 6.5
- Non-DM: not meeting criteria of DM or pre-DM above

For all other endpoints, baseline will be defined as the last available measurement before start of randomised trial medication.

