7.3.1 Primary endpoint analyses

The primary endpoint will be evaluated on the randomised set using a Cox proportional hazards model with treatment, age (continuous), gender, geographical region, baseline status of DM (DM, pre-DM, no DM), LVEF (continuous) and eGFR (CKD-EPI)_{cr} at baseline (continuous) as covariates.

The time to the event of interest will be computed as (event date – randomisation date) + 1. All events observed after randomisation until completion of the planned treatment phase will be included in the analysis. Patients who do not have an event will be censored at the individual end of the planned treatment phase or the last day that the patient was known to be free of the event, whichever is earlier. The time to censoring will be computed as (individual end of the planned treatment phase or the last day known to be free of the event – randomisation date) + 1. For patients who have more than one primary endpoint event during the trial, the time to the first occurrence of the primary endpoint event will be considered for the primary analysis. Only the adjudicated and confirmed events will be used for the primary analysis.

Proprietary confidential information © 2019 Boehringer Ingelheim International GmbH or one or more of its affiliated companies

To detect any heterogeneity in the treatment effect among diabetic patients, pre-diabetic patients and non-diabetic patients, a subgroup analysis will be performed by including the diabetic status by treatment interaction term into the Cox model.

Standard subgroup analyses of the primary endpoint include geographical region, sex, BMI, LVEF, renal function, prognostic factors, age, ethnicity, race and different background therapies etc. More details will be specified in the TSAP.

A sensitivity analysis will be provided based on the TS only including any events up to 30 days after treatment discontinuation.

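### Time to onset of diabetes in pre-DM patients is analysed without baseline HbA1c, and the model's only glycaemic covariate is constant in that subset, which costs power

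*Protocol*

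**What the plan says.** - **Endpoint (Protocol 5.1.2).** "Time to onset of DM (defined as HbA1c $\geq 6.5\%$ or as diagnosed by the Investigator) in patients with pre-DM". Pre-DM means no history of DM, no pre-treatment HbA1c of 6.5 or more, and "a pre-treatment HbA1c value of ≥ 5.7 and < 6.5". Section 7.3 uses the same definition for baseline DM status.
- **Model (Protocol 7.3.2).** "The other time-to-event type of secondary endpoints will be analysed using the same Cox proportional hazards model as the primary analysis".
- **Covariates of that model (Protocol 7.3.1).** The Cox model contains "treatment, age (continuous), gender, geographical region, baseline status of DM (DM, pre-DM, no DM), LVEF (continuous") and baseline eGFR. HbA1c is not among them.
- **Data available (Flow Chart, with footnote 15).** HbA1c is scheduled at Visits 1 and 2 and at most later on-site visits: "HbA1c to be analysed in all patients, e.g. diabetics and non-diabetics".
- **Practice for other endpoints (Protocol 7.3.2 and 7.3.3).** The KCCQ model contains "baseline score by visit, visit by treatment, gender, geographical region and status of DM". The eGFR slope model, the post-treatment eGFR ANCOVA and the MMRMs for further longitudinal endpoints also include the baseline of the variable being measured.
- **Status (Protocol 5.1.2 and 7.2).** Onset of DM lies outside the confirmatory hierarchy and is exploratory.

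**The concern.** The event is largely the crossing of a fixed laboratory threshold. If HbA1c is reported to one decimal, a patient starting at 6.4% is one reading step from the event and a patient starting at 5.7% is eight steps away. The planned model treats the two alike. Its one glycaemic term, DM status, cannot separate them, because everyone in this analysis is pre-DM by definition.

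The protocol treats the same laboratory variable differently elsewhere. Change in HbA1c over time, including in the pre-DM subgroup, is a further endpoint in 5.1.3, and its MMRM in 7.3.3 contains a baseline-by-visit term. The same patients' HbA1c is therefore baseline-adjusted as a continuous outcome and unadjusted as a threshold crossing.

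Omitting a strong predictor from a Cox model moves the treatment hazard ratio toward 1 and reduces power. Randomisation is stratified by DM class and not by HbA1c level within it, so the analysis also makes no allowance for a chance difference in starting HbA1c between the arms.

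**Working it through.** **1. What the documents fix.** Within pre-DM the three-level DM-status factor has one level, so its coefficients cannot be estimated and the term contributes nothing. What remains is treatment, age, gender, region, LVEF and eGFR. This follows from 5.1.2, 7.3 and 7.3.1 read together and needs no assumption.

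**2. The protocol's own figures.** It states no power for onset of DM. Its primary-endpoint figures fix the follow-up used below, so they were checked first.
- Events at HR 0.80, two-sided 0.05, 90% power (Schoenfeld): 4 × (1.960 + 1.282)² / (ln 0.8)² gives 845; the protocol states 841.
- Patients: with hazard −ln 0.9 on placebo, 18 months' uniform accrual, 20 months' follow-up and 841 events, the result is 4125; the protocol states 4126.

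**3. Size of the pre-DM subset.** Section 3.3 sets a minimum of 15%: 0.15 × 4126 = 619. An upper value of 33% was assumed: 0.33 × 4126 ≈ 1361. Section 3.3 also cites a heart-failure trial with about 27% pre-DM, which lies between the two.

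**4. Threshold-crossing simulation.** Assumptions:
- True HbA1c is normal with mean 6.0 and SD 0.35. Screening and baseline readings both lie in 5.7 to 6.4.
- Mean drift is 0.04 per year (SD 0.12).
- Readings are taken at weeks 12, 32, 52, 76, 100, 124 and 148.
- Follow-up is uniform over 20 to 38 months, with death at a rate of 0.06 per year censoring.
- The event is the first reading of 6.5 or more.

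Cox models used Efron ties, with treatment alone and then treatment plus baseline HbA1c, 250 runs per row.

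| n | Reading SD | Drug shift | Patients with event | Power without HbA1c | Power with HbA1c | HR without | HR with |
|---|---|---|---|---|---|---|---|
| 619 | 0.12 | 0.03 | 21% | 16% | 23% | 0.84 | 0.81 |
| 619 | 0.12 | 0.06 | 20% | 47% | 58% | 0.71 | 0.67 |
| 619 | 0.20 | 0.03 | 31% | 16% | 23% | 0.87 | 0.86 |
| 619 | 0.20 | 0.06 | 30% | 46% | 54% | 0.75 | 0.73 |
| 1361 | 0.12 | 0.03 | 21% | 32% | 40% | 0.84 | 0.82 |
| 1361 | 0.12 | 0.06 | 19% | 79% | 93% | 0.71 | 0.67 |
| 1361 | 0.20 | 0.03 | 31% | 29% | 35% | 0.87 | 0.86 |
| 1361 | 0.20 | 0.06 | 30% | 80% | 88% | 0.76 | 0.73 |

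The gain is 6 to 14 points in every row. The Monte Carlo standard error of a single power near 50% is √(0.25/250) = 3.2 points. Both models are fitted to the same data sets, so the differences are steadier than that. The hazard ratio per 0.1 point of baseline HbA1c came out at about 1.7 (SD 0.12) or 1.4 (SD 0.20), a strong predictor in either case.

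**5. Hazard-model simulation.** Here the event hazard was tied directly to baseline HbA1c: HR 1.5 or 2.0 per 0.1 point, treatment HR 0.7 or 0.8, 0.10 events per year at HbA1c 6.0, Breslow ties, 500 runs. Gains ran from 2.8 points (20.6% to 23.4%; n = 619, HR 1.5 per 0.1, treatment HR 0.8) to 29.6 points (56.6% to 86.2%; n = 1361, HR 2.0 per 0.1, treatment HR 0.7). A null run of 800 trials rejected in 4.5% without HbA1c and 2.8% with it, so adjustment does not inflate type I error.

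**6. Other assumption sets.** With true HbA1c centred at 5.9, drift 0.03 per year (SD 0.08), reading SD 0.12 or 0.18 and shifts of 0.03 to 0.08, the gain ran from 3 points, where power was already about 95%, to about 18 points (61% to 79% at n = 1360, shift 0.05, SD 0.12). A separate set, which included runs with investigator-diagnosed events added, gave about 10 to 18 points, 4 points where power was already 94%, and a hazard ratio moving for example from 0.73 to 0.68.

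**The case against.** - **Exploratory status.** No confirmatory decision depends on this endpoint, and the protocol claims no power for it. This stands and limits the stakes to precision and power.
- **The planned test is valid.** A constant covariate drops out harmlessly, and the null run held the 5% level. Chance imbalance in HbA1c within pre-DM is ordinary sampling variation that the confidence interval already covers. This stands too: the defect is inefficiency, not bias in the test.
- **Non-collapsibility.** Hazard ratios with and without HbA1c are different conditional quantities, so the value nearer 1 is not a wrong estimate of the other. That is correct. The planned model is already conditional on several covariates, however, and the loss of power remains on either view.
- **Assumed size.** HbA1c spread, noise, drift and drug effect have no source in the protocol. The simulations also omit the other planned covariates, and most use only the laboratory criterion. The exact figure is therefore uncertain. The direction was the same in every scenario reported, including the set with runs that added investigator diagnoses.
- **One common covariate set, with refinements left to the SAP.** A uniform list for all time-to-event endpoints is a reasonable convention. But 7.3.2 does not leave the model open; it states that it is the same. This is a stated choice, and for this endpoint it keeps a term that cannot work and omits the one that would.

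**Conclusion.** The point holds. The protocol assigns a threshold-crossing HbA1c endpoint in pre-DM patients to a model with no effective glycaemic covariate, although baseline HbA1c is collected.

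Under the threshold-crossing assumptions tabulated above, the loss is about 6 to 14 power points. Across all the assumption sets it ranges from about 3 to 30, and it is small where power is already very high. The treatment hazard ratio sits nearer 1, typically by 0.01 to 0.06.

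These sizes depend on assumed HbA1c distribution, measurement noise, drift, drug effect and pre-DM share. The direction does not depend on a particular choice among them, provided starting HbA1c predicts crossing 6.5%. Type I error, the primary endpoint and the confirmatory hierarchy are unaffected. The change should be made because it recovers information at almost no cost, in a subset that may be as small as 15% of the trial.

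**What to change.** In Protocol 7.3.2, add one sentence: for time to onset of DM, the Cox model replaces baseline DM status by baseline HbA1c (continuous) and keeps the other covariates of the primary model. Baseline HbA1c needs no new definition, because 7.3 already takes the last value before first trial medication for variables not based on creatinine. The SAP should carry the same wording.

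The cost is one line of text and one endpoint whose covariate list differs from the common set. No extra data or visits are required. There is a precedent: Global Amendment 3 added a baseline-eGFR-by-time term to the eGFR slope model so that the slope could vary with the starting value.

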5.3.4.1 Renal function

Urine albumin/creatinine ratio (UACR) in spot urine will be determined and calculated at the central laboratory.

The estimated glomerular filtration rate (eGFR) will be derived from serum creatinine values, age, sex and race based on the CKD-EPI equation [[R12-1392](#)]:

$$\text{GFR} = 141 \times \min(\text{Scr} / \kappa, 1)^\alpha \times \max(\text{Scr} / \kappa, 1)^{-1.209} \times 0.993^{\text{Age}} \times 1.018 \text{ [if female]} \times 1.159 \text{ [if black]}$$

where:

Scr is serum creatinine in mg/dL,

κ is 0.7 for females and 0.9 for males,

α is -0.329 for females and -0.411 for males,

min indicates the minimum of Scr / κ or 1, and

max indicates the maximum of Scr / κ or 1.

Proprietary confidential information © 2019 Boehringer Ingelheim International GmbH or one or more of its affiliated companies

The race of the patient will be entered because of potential differences due to race. The CKD-EPI equation considers the race as an adjustment factor, therefore the race must be known for accurate estimation.

In case of an eGFR loss of $\geq 40\%$ since baseline, or when the eGFR drops to < 15 mL/min/1.73 m² for patients with an eGFR ≥ 30 mL/min/1.73 m² at baseline (< 10 mL/min/1.73 m² for patients with an eGFR < 30 mL/min/1.73 m² at baseline); an additional visit between 30 days to preferably 60 days after detection should be scheduled (unless detected at the EOT visit at trial end) to collect a blood sample for repeat central analysis of creatinine for calculation of the eGFR. If a signal of abnormal creatinine or eGFR is reported to the site by others (e.g. treating physicians from local labs), an additional sample should be sent to central lab, and if it is still abnormal, another sample should be sent to central lab between 30 days and preferably 60 days.

Kidney function will be classified as described in the table below ([Table 5.3.4.1:1](#)):

Table 5.3.4.1: 1 Classification of kidney function

CKD stage	eGFR
1	≥ 90
2	60-89
3a	45-59
3b	30-44
4	15-29
5	< 15

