Figure 7.2: 1 Hierarchical analysis of trial in HFpEF (1245.110) and the parallel trial in HFrEF (1245.121) showing the alpha-spending at the final analysis.

The other secondary endpoints will be evaluated in an exploratory manner.

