7.7 DETERMINATION OF SAMPLE SIZE

For the sample size calculation, a yearly event rate in the placebo group of 10% is assumed. The assumption is based on the CHARM-Preserved study and part of the TOPCAT study from the Americas [[R07-4374](#), [R16-1458](#)]. The annual event rates in CHARM-Preserved were 8.1% in the candesartan group and 9.1% in the placebo group. The annual rates from the Americas in the TOPCAT study were 10.4 in the spironolactone group and 12.6 in the placebo group.

The trial is designed to achieve a power of 90% for a two sided test at level $\alpha = 0.05$.

Proprietary confidential information © 2019 Boehringer Ingelheim International GmbH or one or more of its affiliated companies

The following table presents the number of required events together with the number of to be randomised and treated patients assuming an accrual period of 18 months and a follow-up period of 20 months for different assumed true hazard ratios. However, the follow-up period is not fixed but the trial will continue until the necessary number of events has been observed, which are confirmed by the adjudication committee.

The drop-out rate from the trial is assumed to be low (< 1% per year) and is therefore not further considered for the determination of sample size.

Table 7.7: 1 Sample size calculation – not including interim analyses:

Yearly event rate for HHF+CV Death (Placebo)	Hazard ratio	Number of events for 90% power for HHF+CV Death	Number of patients for 18 months accrual and 20 months follow up
10%/Year	0.70	331	1710
10%/Year	0.75	509	2562
10%/Year	0.80	841	4126
10%/Year	0.85	1601	7656
10%/Year	0.90	3814	17814

A hazard ratio of 0.8 was chosen as a conservative estimate based on the results of the EMPA-REG OUTCOME trial described in [Section 1.2.3](#)

Therefore, at least 841 confirmed primary events should be observed and at least 4126 patients should be randomised and treated in order to achieve a power of 90% assuming a true hazard ratio of 0.8.

Including interim analysis with Hwang-Shih-deCani alpha spending with gamma=8 at 60% of information will diminish the power only slightly to 89.98%.

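### The Cox model fixed for the kidney composites leaves out centrally measured baseline UACR; the analysis is valid, and adding log UACR would make it modestly more efficient

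*Protocol*

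**What the plan says.** All references are to the current protocol text (revision of 20 Nov 2019).

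- Section 5.1.2 lists the kidney composite first among the other secondary endpoints: "Time to first occurrence of chronic dialysis or renal transplant or sustained* reduction of" at least 40% in eGFR, or a sustained eGFR below a threshold that depends on baseline.
- Section 7.3.2 fixes its model: "The other time-to-event type of secondary endpoints will be analysed using the same Cox proportional hazards model as the primary analysis".
- Section 7.3.1 gives that model's covariates: a Cox "hazards model with treatment, age (continuous), gender, geographical region, baseline status of DM (DM, pre-DM, no DM), LVEF (continuous) and eGFR" at baseline. UACR is not in the list.
- Section 7.3.3 applies the same Cox model to further time-to-event endpoints. These include the three composites in Section 5.1.3 that combine the eGFR criteria with CV death, all-cause death, or CV death and HHF.
- Section 5.3.4.1: "Urine albumin/creatinine ratio (UACR) in spot urine will be determined and calculated at the central laboratory". The Flow Chart schedules it at Visit 1 (screening) and Visit 2 (randomisation), before treatment starts.
- On status, Section 5.1.2 heads the list "Other secondary endpoints (not part of confirmatory testing hierarchy on trial level) are the following", and Section 7.2 adds that "The other secondary endpoints will be evaluated in an exploratory manner".

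**The concern.** The covariate list was written for CV death and HHF and carried over unchanged to a kidney outcome. Baseline eGFR is in it; baseline albuminuria is not. If albuminuria predicts the kidney composite beyond eGFR and diabetes status, a Cox model without it estimates a hazard ratio somewhat nearer 1 than the model with it, and so has a little less power.

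The protocol takes the kidney question seriously. Section 1.2.3 says that slowing of renal decline will be tested further through the eGFR slope and the composite renal endpoints. Elsewhere it fits models to the outcome: Global Amendment 3 added a baseline-eGFR-by-time term to the slope model, and the KCCQ model contains the baseline score by visit. The kidney composites received no such term, although the variable is already collected. What is at stake is precision on exploratory endpoints.

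**Working it through.** **1. The protocol's own design figure.** Section 7.7 states "The trial is designed to achieve a power of 90% for a two sided test at level" 0.05, with HR 0.80, 841 events and 4126 patients, for the primary endpoint.

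- Events: 4(z₀.₉₇₅ + z₀.₉₀)² / (ln HR)² = 4 × (1.960 + 1.282)² / (ln 0.80)² = 42.03 / 0.04979 = 844.1, rounded up to 845. This is close to 841.
- Patients: for hazard λ, p = 1 − [exp(−λa) − exp(−λb)] / [λ(b − a)], with a = 20/12 and b = 38/12 years. With λ = −ln 0.9 on placebo and 0.8λ on active treatment, the mean p is 0.2039. Then 841 / 0.2039 ≈ 4125, against 4126 stated.

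The protocol gives no such figure for the kidney composite, so the rest uses assumed ranges.

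**2. Effect of leaving UACR out.** Let the hazard be λ₀·exp(βA + bU), where A is treatment and U is standardised log UACR, N(0,1), independent of A. Accrual and follow-up are as in Section 7.7. Let β* be the large-sample limit of the Cox treatment estimate without U. The standard error of the log HR is almost the same with and without U (step 4), so relative efficiency is (β*/β)². Approximate power is Φ(|β*|√d/2 − 1.96), with d events.

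Assumed: UACR-conditional HR exp(β) = 0.80; placebo risk 0.5 to 4% per year; UACR hazard ratio 1.5 to 3 per SD beyond the other covariates. Each cell gives the HR without UACR, then the relative efficiency.

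| Placebo risk/year | 1.5 per SD | 2 per SD | 3 per SD |
|---|---|---|---|
| 0.5% | 0.8002; 0.998 | 0.8006; 0.993 | 0.8022; 0.976 |
| 1% | 0.8004; 0.996 | 0.8012; 0.987 | 0.8041; 0.954 |
| 2% | 0.8007; 0.992 | 0.8024; 0.974 | 0.8076; 0.917 |
| 4% | 0.8014; 0.984 | 0.8045; 0.950 | 0.8132; 0.859 |

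Power at the maximum of 6000 patients, with against without UACR:

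- 2% per year, 2 per SD, 256 events: Φ(0.2231 × 16/2 − 1.96) = 43.0% against Φ(0.2201 × 16/2 − 1.96) = 42.1%.
- 4% per year, 2 per SD: 70.5% against 68.3%.
- 4% per year, 3 per SD (the extreme corner, 487 events): 69.2% against 62.7%.

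**3. Simulation with eGFR in both models.** 24 data sets of 100,000 patients per scenario, follow-up 20 to 38 months, 6% per year death as censoring, treatment HR 0.75. Ratio of squared z for treatment, with against without log UACR:

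| Event rate/year | log HR 0.5 per SD (HR 1.65) | 0.8 (HR 2.23) | 1.1 (HR 3.00) |
|---|---|---|---|
| 1.5% | 1.013 | 1.018 | 1.071 |
| 3% | 1.017 | 1.062 | 1.128 |

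In the last cell the HR is 0.765 without UACR and 0.752 with it: (ln 0.752 / ln 0.765)² = (0.2850 / 0.2679)² ≈ 1.13. The two approaches agree. For example, step 2 at 2% per year and 3 per SD gives 1/0.917 = 1.09, between 1.071 and 1.128.

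**4. Validity.** 600 simulated trials of 6000 patients each, 2% per year, UACR effect 2 per SD.

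- Conditional HR 0.80: the standard error of the log HR was 0.1265 in both models (about 255 events).
- HR 1: the mean HR without UACR was 0.994. One-sided rejection at nominal 2.5% was 2.8% without UACR and 3.0% with it. The simulation error is √(0.025 × 0.975/600) = 0.6 points, so both are compatible with 2.5%.

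**The case against.** The case for leaving the model alone is a fair one. One common covariate set for all time-to-event endpoints is simple, legitimate pre-specification. UACR is not a stratification factor, so the model omits nothing that the randomisation used. Baseline eGFR and diabetes status are already adjusted for, and any overlap between them and UACR reduces what UACR can add. A UACR-adjusted analysis may also sit in the TSAP, which was not available here. All of this stands, and it makes the point a refinement rather than an error. It does not remove the gain from the model that Sections 7.3.2 and 7.3.3 do fix.

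A reader might infer more than the documents support:

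- *That the planned hazard ratio is biased.* It is not. The shift is non-collapsibility: the model validly estimates the hazard ratio conditional on its listed covariates, and the test keeps its level.
- *That the loss matters more because kidney events are few.* The relative loss shrinks as events become rarer. At 2 per SD, relative efficiency without UACR is 0.950 at 4% per year and 0.993 at 0.5%.
- *That a confirmatory conclusion is at risk.* The kidney composite is outside the trial-level hierarchy and exploratory. The pooled meta-analyses have their own plans (Section 7.3.6).
- *That the protocol contradicts itself.* No section promises adjustment for UACR.

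**Conclusion.** The point holds as an optional improvement. The Cox model fixed for the kidney composites omits a baseline measurement that is already collected, and including it would improve efficiency modestly.

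With 1.5 to 3% events per year and a hazard ratio of about 1.6 to 3 per SD of log UACR, the information gain is about 1 to 13%. For effects up to 2 per SD this is about 0 to 2 power points, and at a conditional HR of 0.80 the estimate moves by at most 0.005. Gains near the top of the range need roughly a threefold hazard per SD of log UACR beyond eGFR and diabetes status. In the most extreme case examined (4% per year, 3 per SD) the loss is about 6 to 7 power points.

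The event rates, the UACR effects and the treatment hazard ratios for this endpoint are assumptions; the documents give none of them. The figures are for the kidney composite. The three further composites were not computed separately: they add deaths or HHF, and how strongly UACR predicts those combined outcomes is also undocumented.

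**What to change.** Before unblinding, add to Section 7.3.2: 'For the kidney composite, log-transformed baseline UACR is added as a continuous covariate to the Cox model.' Apply the same to the three kidney composites in Section 5.1.3, through Section 7.3.3 or the TSAP.

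State a simple rule for missing baseline UACR. Section 7.3 already takes the last value before treatment as baseline for measures other than creatinine and eGFR, so Visit 1 can stand in for a missing Visit 2 value. Only patients with neither need a rule, for example the overall median of the log value, set without regard to treatment.

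The cost is one or two sentences and that rule. No new data, visits or patients are needed, and the testing hierarchy does not change.
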